11.5 ECOG-ACRIN Sample Tracking System

It is **required** that all specimens submitted on this trial be entered and tracked using the ECOG-ACRIN Sample Tracking System (STS). The software will allow the use of either 1) an ECOG-ACRIN user-name and password previously assigned (for those already using STS), or 2) a CTSU username and password.

When you are ready to log the collection and/or shipment of the specimens required for this study, please access the Sample Tracking System software by clicking <https://webapps.ecog.org/Tst>

**Important:** Any case reimbursements associated with specimen submissions will not be credited if specimens are not logged into STS. Additionally, please note that the STS software creates pop-up windows, so you will need to enable pop-ups within your web browser while using the software. A user manual and interactive demo are available by clicking this link:  
<http://www.ecog.org/general/stsinfo.html>.

Please take a moment to familiarize yourself with the software prior to using the system.

An STS generated shipping manifest form should be shipped with all specimen submissions.

Please direct your questions or comments pertaining to the STS to [[contact]](mailto:[contact]).

Rev.10/16

### **Study Specific Notes**

The exact date and time of entinostat/placebo administration and of PK plasma sample collection must be entered into the ECOG-ACRIN Sample Tracking System, and provided with the documentation submitted with the plasma samples.

Generic Specimen Submission Form (#2981) will be required only if STS is unavailable at time of specimen submission. Notify the laboratory of the shipment by faxing a copy of the completed form to the laboratory. Indicate the appropriate Lab ID# on the submission form:

- ECOG-ACRIN CBPF
- [name] Laboratory
- Covance Central Laboratory Services

**NOTE:** Covance Central Laboratory Services will not be utilizing the STS to confirm receipt.

Retroactively enter all specimen collection and shipping information when STS is available.

## 11.6 Reimbursements for Population Pharmacokinetic Plasma Sample Submissions

Rev. 9/17

### 11.6.1 Institutional Reimbursements

To offset research-related costs associated with the collection and submission of the plasma samples at the four time points outlined above in Section [11.4](#), institutions are eligible to receive reimbursements. Please see the Funding Sheet for further details. Plasma samples must be collected and submitted to trigger payment. Receipt of the plasma samples will be verified prior to the release of funds.

**NOTE:** Neither patients nor their insurance companies are to be billed for the collection or submission of the pharmacokinetic plasma samples.

Distribution of the reimbursements requires:

- Submission of the required pharmacokinetic plasma samples using the ECOG-ACRIN Sample Tracking System (STS) [Refer to Section [11.5](#) for STS requirements]
- Receipt and verification of the plasma samples by Covance Central Laboratory Services

#### 11.6.2 Patient Vouchers

Vouchers will be distributed to institutions for use by the patients to off-set expenses incurred during the 2-5 hour time period of the cycle 1, day 1 pharmacokinetic plasma sample collections. Vouchers will be sent to the contact person and institutional shipping address provided in OPEN.

Vouchers are being provided by Syndax.

Rev.4/15

#### 11.7 Use of Specimens in Research

Blood will be distributed to investigators for the laboratory research studies defined in Section [12](#).

Specimens from patients who consented to allow their specimens to be used for future ECOG-ACRIN approved research studies will be retained in an ECOG-ACRIN designated central repository.

For this trial, specimens will be retained at the ECOG-ACRIN Central Biorepository and Pathology Facility.

Specimens submitted will be processed to maximize their utility for current and future research projects. Tissue processing may include, but not limited to, extraction of DNA and RNA and construction of tissue microarrays (TMAs). DNA and plasma (if appropriate) will be isolated from the submitted peripheral blood specimens.

Any residual blocks will be available for purposes of individual patient management on specific written request.

Rev.10/16

Residuals/derivatives from the plasma samples submitted for the population pharmacokinetic studies will not be retained for future research studies.

If future use is denied or withdrawn by the patient, the specimens will be removed from consideration for use in any future research study. Pathology materials may be retained for documentation purposes or returned to the site. All other specimens will be destroyed per guidelines of the respective repository.

#### 11.8 Sample Inventory Submission Guidelines

Inventories of all samples submitted from institutions will be tracked via the ECOG-ACRIN STS and receipt and usability verified by the receiving laboratory. Inventories of samples forwarded and utilized for approved laboratory research studies will be submitted by the investigating laboratories to the ECOG-ACRIN Operations Office – Boston on a monthly basis in an electronic format defined by the ECOG-ACRIN Operations Office – Boston.

## 12. Correlative Studies

The results of these studies are for the purposes of the trial only and will not be returned to the site or reported to the patient.

### 12.1 Acute Change in Protein Lysine Acetylation as a Predictor of Benefit from Entinostat

This analysis will be performed in the laboratory of [name] at NCI/NIH (See Section 12.2). Protein lysine acetylation will be measured by multiparameter flow cytometry in peripheral blood mononuclear cells (PBMCs; CD19+ B cells, CD3+ T cells, and CD14+ monocytes). [name] and her team have developed and published the method to be utilized to perform this correlative analysis, which includes determination of the stability of acetylation in PBMC samples. In addition the team has been coauthors on four clinical trials, including ENCORE 301, in which the flow cytometric pharmacodynamic assay has been performed.

Peripheral blood mononuclear cells (PBMCs) offer an opportunity to assess pharmacodynamic effects of entinostat and to correlate the observed effects with breast cancer outcome. In PBMCs, the effects of entinostat will be measured by global protein acetylation using multi-parameter flow cytometry.

We hypothesize that patients with increased protein lysine acetylation in the two weeks after initiating therapy will have a prolonged PFS compared to those without changes in protein lysine acetylation.

To briefly review, ENCORE 301 collected PBMCs for assessment of lysine acetylation prior to therapy, and post-therapy on Days 8 and 15 using an assay developed by the [name] Laboratory, NCI/NIH. Protein lysine acetylation in the combined therapy subgroup was associated with a striking improvement in PFS across all cell types. In EE-treated hyperacetylators versus those with acetylation below the median, median PFS was 8.5 versus 2.7 months (HR=0.32, 95% CI 0.13, 0.79) (B cells); 6.6 versus 3.6 months (HR=0.44, 95% CI 0.18, 1.08) (T cells); and 6.2 versus 3.6 months (HR=0.50, 95% CI 0.21, 1.20) (monocytes).

We will use the identical methodology, central laboratory ([name] Laboratory, NCI/NIH), and timing (Day 15) for the acetylation studies planned in E2112. While our data will not independently contribute to the validation effort, it will further expand the pharmacodynamic data and add measurably to our interpretation of the clinical data.

Rev.10/16

### 12.2 Population Pharmacokinetics

The population pharmacokinetic analysis for entinostat will be used to describe the pharmacokinetics of entinostat in patients and to assess the effects of patient factors on the entinostat pharmacokinetics. Specific details for this analysis will be provided in a separate population pharmacokinetic analysis plan.

### 12.3 Future Research Studies

The following correlative studies are proposed as outlined below. Final analysis of the proposed studies requires the results of the parent study. When sufficient information is available from the parent study a full correlative science proposal or amended protocol document detailing the scientific hypothesis, research plan,

assay methods for use of the biospecimens, and a formal statistical analysis plan with adequate power justification will be submitted to and reviewed by CTEP.

#### 12.3.1 Pharmacogenomics

Genomic DNA isolated from whole blood at baseline can be used to genotype candidate genes that may affect pharmacodynamic effects of response and toxicity. We will store the sample obtained at baseline for potential future analyses in the event that further information becomes available from the literature about promising candidate genes that may predict response to exemestane and/or entinostat.

#### 12.4 Lab Data Transfer Guidelines

The data collected on the above mentioned laboratory research studies will be submitted electronically using a secure data transfer to the ECOG-ACRIN Operations Office – Boston by the investigating laboratories on a quarterly basis or per joint agreement between ECOG-ACRIN and the investigator.

### 13. Electronic Data Capture

Please refer to the E2112 Forms Completion Guidelines for the forms submission schedule. Data collection will be performed exclusively in Medidata Rave.

This study will be monitored by the CTEP Data Update System (CDUS) version 3.0. Cumulative CDUS data will be submitted quarterly from the ECOG-ACRIN Operations Office – Boston to CTEP by electronic means.

#### 13.1 Records Retention

FDA regulations (21 CFR 312.62) require clinical investigators to retain all trial-related documentation, including source documents, long enough to allow the sponsor to use the data to support marketing applications.

This study will be used in support of a US marketing application (New Drug Application), all records pertaining to the trial (including source documents) must be maintained for:

- two years after the FDA approves the marketing application, or
- two years after the FDA disapproves the application for the indication being studied, or
- two years after the FDA is notified by the sponsor of the discontinuation of trials and that an application will not be submitted.

Please contact the ECOG-ACRIN Operations Office – Boston prior to destroying any source documents.

### 14. Patient Consent and Peer Judgment

Current FDA, NCI, state, federal and institutional regulations concerning informed consent will be followed.

**Appendix I**

**Pathology Submission Guidelines**

The following items are included in Appendix I:

1. Guidelines for Submission of Pathology Materials  
(instructional sheet for Clinical Research Associates [CRAs])
2. Instructional memo to submitting pathologists
3. ECOG-ACRIN Generic Specimen Submission Form (#2981)

Rev. 4/15

Rev. 9/17

### Guidelines for Submission of Pathology Materials

E2112 A Randomized Phase III Trial of Endocrine Therapy plus Entinostat/Placebo in Patients with Hormone Receptor-Positive Advanced Breast Cancer

#### Instructions:

#### 1. Pathology submissions:

- Representative primary tumor FFPE block
- Representative metastatic tumor FFPE block

**NOTE:** If blocks are unavailable for submission, cores and slides are to be submitted. All cores and slides must be adequately labeled, with slides numbered sequentially in the order cut. Alternative submission requirements:

- One (1) H&E slide, and
- Twenty (20) 4 µm unstained air-dried plus slides, and
- One (1) or more core punches (minimum of 4mm diameter). If core punch tool is unavailable, request core punch kit from the ECOG-ACRIN CBPF ([name]). Adequately label every slide and core submitted.

If these criteria cannot be met, please contact the ECOG-ACRIN CBPF ([[contact]](mailto:[contact])) to obtain alternative submission requirements.

#### 2. The following items are to be included with the pathology materials.

- Copy of the surgical pathology report and surgical procedure report.
- STS generated shipping manifest form

**NOTE:** Adequate patient identifying information must be included with every submission. It is strongly recommended that full patient names be provided. The information will be used only to identify patient materials, for interactions between the ECOG-ACRIN CBPF, the central testing laboratory and the site, and will help to expedite any required communications with the institution (including site pathologists).

**MEMORANDUM**

**TO:** \_\_\_\_\_  
(Submitting Pathologist)

**FROM:** [name]., Chair  
ECOG-ACRIN Laboratory Science and Pathology Committee

**DATE:** \_\_\_\_\_

**SUBJECT:** Submission of Pathology Materials for E2112: A Randomized Phase III Trial of Endocrine Therapy plus Entinostat/Placebo in Patients with Hormone Receptor-Positive Advanced Breast Cancer.

A patient has been entered onto an ECOG-ACRIN protocol by \_\_\_\_\_ (ECOG-ACRIN Investigator). This protocol requires the submission of pathology materials for banking for future undefined research.

Return the surgical pathology report(s), the slides and/or blocks and any other required material to the Clinical Research Associate (CRA). The CRA will forward all required pathology material to the ECOG-ACRIN Central Biorepository and Pathology Facility (CBPF).

Blocks and slides submitted for this study will be retained at the ECOG-ACRIN CBPF for undefined future research studies. Paraffin blocks will be returned upon written request for purposes of patient management. If you have any questions regarding this request, please contact the ECOG-ACRIN CBPF at [name], or by [contact].

The ECOG-ACRIN CRA at your institution is:

Name: \_\_\_\_\_

Address: \_\_\_\_\_

Phone: \_\_\_\_\_

Thank you.

**Institution Instructions:** This form is to be completed and submitted with **all specimens** ONLY if the Sample Tracking System (STS) is not available. **Use one form per patient, per time-point.** All specimens shipped to the laboratory must be listed on this form. Enter all dates as MM/DD/YY. Keep a copy for your files. Retroactively log all specimens into STS once the system is available. **Contact the receiving lab to inform them of shipments that will be sent with this form.**

**Protocol Number** \_\_\_\_\_ **Patient ID** \_\_\_\_\_ **Patient Initials** Last \_\_\_\_\_ First \_\_\_\_\_

**Date Shipped** \_\_\_\_\_ **Courier** \_\_\_\_\_ **Courier Tracking Number** \_\_\_\_\_

**Shipped To (Laboratory Name)** \_\_\_\_\_ **Date CRA will log into STS** \_\_\_\_\_

**FORMS AND REPORTS:** Include all forms and reports as directed per protocol, e.g., pathology, cytogenetics, flow cytometry, patient consult, etc.

Required fields for all samples				Additional fields for tissue submissions				Completed by Receiving Lab
Protocol Specified Timepoint:								
Sample Type <small>(fluid or fresh tissue, include collection tube type)</small>	Quantity	Collection Date and Time 24 HR		Surgical or Sample ID	Anatomic Site	Disease Status <small>(e.g., primary, mets, normal)</small>	Stain or Fixative	Lab ID

Fields to be completed if requested per protocol. Refer to the protocol-specific sample submissions for additional fields that may be required.					
Leukemia/Myeloma Studies:	Diagnosis	Intended Treatment Trial	Peripheral WBC Count (x1000)	Peripheral Blasts %	Lymphocytes %
Study Drug Information:	Therapy Drug Name	Date Drug Administered	Start Time 24 HR	Stop Time 24HR	
Caloric Intake:	Date of Last Caloric Intake		Time of Last Caloric Intake 24HR		

**CRA Name** \_\_\_\_\_ **CRA Phone** \_\_\_\_\_ **CRA Email** \_\_\_\_\_

**Comments** \_\_\_\_\_

---

**A Randomized Phase III Trial of Endocrine Therapy plus Entinostat/Placebo in Patients  
with Hormone Receptor-Positive Advanced Breast Cancer**

**Appendix II**

**Patient Thank You Letter**

We ask that the physician use the template contained in this appendix to prepare a letter thanking the patient for enrolling in this trial. The template is intended as a guide and can be downloaded from the ECOG web site at <http://www.ecog.org>. As this is a personal letter, physicians may elect to further tailor the text to their situation.

This small gesture is a part of a broader program being undertaken by ECOG-ACRIN and the NCI to increase awareness of the importance of clinical trials and improve accrual and follow-through. We appreciate your help in this effort.

---

[PATIENT NAME]

[DATE]

[PATIENT ADDRESS]

Dear [PATIENT SALUTATION],

Thank you for agreeing to take part in this important research study. Many questions remain unanswered in cancer. With the help of people like you who participate in clinical trials, we will achieve our goal of effectively treating and ultimately curing cancer.

We believe you will receive high quality, complete care. I and my research staff will maintain very close contact with you. This will allow me to provide you with the best care while learning as much as possible to help you and other patients.

On behalf of **[INSTITUTION]** and the ECOG-ACRIN Cancer Research Group, we thank you again and look forward to helping you.

Sincerely,

[PHYSICIAN NAME]

**A Randomized Phase III Trial of Endocrine Therapy plus Entinostat/Placebo in Patients  
with Hormone Receptor-Positive Advanced Breast Cancer**

**Appendix III**

**Patient Pill Calendar**

**NOTE TO SITES:** Local study teams may use a different calendar format as long as all drug dates/doses are recorded for study reporting/data completion. These should be shared with the Protocol Chair/Study Liaison, and approved by local IRBs per local guidelines, prior to use.

**Pill Calendar Directions**

1. Take your scheduled dose of each pill.
2. If you forget, the missed pills will not be taken later.
3. Please bring the empty bottle or any leftover tablets and your pill calendar to your next clinic visit.

**Patient Pill Calendar-Exemestane and Entinostat/Placebo**

This is a calendar on which you are to record the time and number of pills you take each day for the study. You should take your scheduled dose of each pill. If you develop any side effects, please record them and anything you would like to tell the doctor in the space provided.

Instructions:

Exemestane: Take by mouth once every day with food.

Dose of each pill: 25 mg

Number of pills to take at each dose: 1

Total dose to take each day: 25 mg

Rev.10/16

Entinostat/Placebo: Take by mouth once each week on an empty stomach (either 1 hour before and 2 hours after meals).

Dose of each pill: \_\_\_\_\_

Number of pills to take at each dose: \_\_\_\_\_

Total dose to take each week: \_\_\_\_\_

Please bring this study diary/calendar and your bottle of entinostat/placebo to each study visit.

CYCLE DAY	Date			Exemestane		Entinostat/ Placebo		Use the space below to make notes about things you would like to tell the doctor (including unusual symptoms you experience, other medicine you have taken and anything else you think would be of interest.)
	(Month / Day / Year)	# pills	Time	# pills	Time			
1				1				
2				1				
3				1				
4				1				
5				1				
6				1				
7				1				
8				1				
9				1				
10				1				
11				1				
12				1				
13				1				
14				1				
15				1				
16				1				
17				1				
18				1				
19				1				

CYCLE DAY	Date			Exemestane		Entinostat/ Placebo		Use the space below to make notes about things you would like to tell the doctor (including unusual symptoms you experience, other medicine you have taken and anything else you think would be of interest.)
	(Month / Day / Year)			# pills	Time	# pills	Time	
20				1				
21				1				
22				1				
23				1				
24				1				
25				1				
26				1				
27				1				
28				1				

---

**A Randomized Phase III Trial of Endocrine Therapy plus Entinostat/Placebo in Patients with Hormone Receptor-Positive Advanced Breast Cancer**

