6.2.4 Adherence

The ECOG-ACRIN Medication Adherence Scale Modified from the Morisky Index will be administered to understand the reasons for non-adherence to protocol therapy. There will be one Medication Adherence Scale form completed for each agent (entinostat /placebo and exemestane). The Medication Adherence Scale measures the likelihood that a patient will take prescribed medications. The Medication Adherence Scale has been validated against medication pill count methods of assessing compliance and used in a variety of settings. It is an 8-item measure with a Likert response scale. The minimal detectable change has been defined as 1.98 points (Muntner).

Patient’s adherence to protocol therapy will be quantified using the pill count (entinostat/placebo) and diary (exemestane) methods. Patients will be instructed to bring their medication bottles and diaries to clinic visits. Clinic or pharmacy staff will count the number of remaining entinostat/placebo pills or note the number of exemestane pills as taken on the pill diary, and will calculate the number of pills taken using a treatment form.

Rev. Add5  
Rev. Add7

Rev.4/15  
Rev.10/15  
Rev. 10/16  
Rev. Add5

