PROMIS Fatigue, FAACT, FACIT-D: Baseline (before Cycle 1 Day 1), end of Cycle 3, end of Cycle 6, end of Cycle 12, at end of protocol treatment, including treatment discontinuation for any reason (i.e., toxicity, progression, completion of protocol therapy) and 4 weeks after end of protocol treatment, including treatment discontinuation for any reason (i.e., toxicity, progression, completion of protocol therapy).

Rev. 10/16 The ECOG-ACRIN Medication Adherence Scale Modified from the Morisky Index: end of Cycle 3, end of Cycle 6, end of Cycle 12, and at  
Rev. Add7 end of protocol treatment, including treatment discontinuation for any reason (i.e. toxicity, progression, completion of protocol therapy).  
Please note there will be one Medication Adherence Scale form completed for each agent (entinostat/placebo and exemestane).

FACT-G: Baseline (before Cycle 1 Day 1), end of Cycle 3, end of Cycle 6, end of Cycle 12, and at end of protocol treatment, including treatment discontinuation for any reason (i.e. toxicity, progression, completion of protocol therapy).

8. The FBSI will be administered at baseline, end of each cycle for the first six months after randomization, and then at the end of Cycles 8, 10, and 12. After Cycle 12, the FBSI will be administered on the same schedule as Tumor assessments until disease progression.
9. Pill counts for entinostat/placebo and diaries for exemestane should be collected at the end of each cycle until discontinuation of study treatment.
10. Repeat any test not done  $\leq$  the prior 28 days.
11. Every 3 months if patient is  $< 2$  years from study entry, every 6 months if patient is 2-5 years from study entry, and annually if patient is  $>5$  years from study entry. No specific requirements if patient is more than 10 years from study entry.
12. Tumor assessments are to be done up to (and including) the assessment which shows first progression of disease. If patient discontinues treatment due to reasons other than disease progression, concomitant medication and tumor assessments should be performed until disease progression on the following schedule: Every 3 months if patient is  $< 2$  years from study entry, every 6 months if patient is 2-5 years from study entry, and annually if patient is  $>5$  years from study entry. No specific requirements if patient is more than 10 years from study entry.

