#### 9.7 Adherence to Protocol Therapy

Another secondary objective of the study is to measure adherence to protocol therapy. Patient's adherence to protocol therapy will be quantified using pill count (entinostat/placebo) and diary methods (exemestane). The number of pills a patient has taken will be recorded for every cycle (4 weeks). Patients will be instructed to bring their medication bottles (entinostat/placebo) and diaries (exemestane) with them for clinic visits. Clinic or pharmacy staff will count the number of remaining pills (entinostat/placebo) or pill diary doses taken (exemestane), and will calculate the number of pills taken using a treatment form. As administration of entinostat/placebo is weekly, it will be 0-4 doses per cycle.

Dose reduction (from 5mg to 3mg) is allowed for entinostat/placebo due to toxicity in the trial. If more than two consecutive doses of entinostat/placebo, or > two doses of entinostat/placebo per cycle are omitted due to toxicity, the patient will be permanently discontinued from protocol therapy. For exemestane, it will be administered once daily in each cycle, it will be 0-28 pills per cycle. Exemestane dose reductions are not allowed. If exemestane administration is held for > 7 days due to any reason, patient will be considered permanently off protocol treatment.

The adherence score will be calculated as the proportion of the total number of pills a patient actually took over the whole treatment period divided by the total

number of pills a patient should have taken. The strength of doses will be taken into account and the reduced dose of 3mg will be counted as 0.6 full dose (5mg) in adherence score calculation. The timing of doses will not be considered in the study. Data about adherence to protocol therapy will be collected for exemestane and entinostat /placebo separately for each arm. The adherence score will be calculated for each patient for each agent (exemestane and entinostat /placebo) separately. For the evaluation of each agent, patients will be categorized into 3 groups based on the adherence score. An adherence score of > 85% will be considered as high adherence, and an adherence score of < 65% will be considered as low adherence, and patients with an adherence score of 65%-85% will be considered as medium adherence.

Rev. Add7

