#### 9.7.2 Analysis plan for adherence

The analysis time for adherence endpoint is at about 70 months after study activation (same time as final OS analysis). All patients who receive at least one dose of protocol therapy and have sufficient adherence data will be included in the analysis.

The distribution of the adherence score for each agent will be displayed via box-and-whisker plot. The proportion of high, medium and low adherence to each agent will be calculated along with the binomial exact 95% confidence interval. The proportion of high adherence to entinostat and placebo will be compared between arms A and B using Fisher exact test. The proportion of adherence to exemestane will be compared between treatment arms using Fisher exact test as well. In addition, the adherence score for each cycle will be calculated for each agent and plot by treatment cycle to examine how adherence changes over time. The reasons for non-adherence will be summarized for each agent on each arm. The agreement on adherence level during a treatment period will be examined between the pill counts method and the Medication Adherence Scale method.

As an exploratory analysis, the association between baseline HRQL (categorized as good, fair, poor) and adherence to protocol therapy (categorized as high, medium and low adherence or dichotomized as good or poor) during the whole treatment period will be examined in each treatment arm using Fisher exact test. Multivariable logistic regression analysis will be conducted to identify the baseline factors which can predict high adherence. The covariates will include HRQL and other patient demographics and disease characteristics, such as age at diagnosis, ECOG PS, disease stage, prior therapy, et al.

The association between adherence to protocol therapy during the whole treatment period (categorized as high, medium or low) and HRQL (continuous score) at one-month after treatment discontinuation will be examined using ANOVA test and linear regression analysis, adjusting for HRQL at baseline and other demographic and disease characteristics.

Another exploratory analysis is to examine the association between the occurrence of toxicity in the first two cycles and adherence to entinostat after cycle 2 in patients on arm A.

In all analyses, P-values will be two-sided. A level of 5% will be considered statistically significant. No adjustment will be made for multiple comparisons.

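### The template diary that feeds the exemestane adherence score has one pill already printed for each of the 28 days, so missed doses may be recorded as taken

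*Combined protocol and SAP*

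**What the plan says.** Measuring adherence is secondary objective 2.2.7. Section 9.7 defines a score for each agent: pills taken over the whole treatment period divided by pills due. Above 85% is high, below 65% is low, and the range between is medium.

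The two agents have different data sources. Section 7, footnote 9, states: "Pill counts for entinostat/placebo and diaries for exemestane should be collected at the end of each cycle until discontinuation of study treatment". For exemestane, Section 6.2.4 has staff "or note the number of exemestane pills as taken on the pill diary", and Section 9.7 has them use "or pill diary doses taken (exemestane), and will calculate the number of pills taken using a treatment form". Only entinostat/placebo has its remaining tablets counted.

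Section 9.7.2 plans the proportions in each category, a plot of the score by cycle, and a comparison of arms: "The proportion of adherence to exemestane will be compared between treatment arms using Fisher exact test as well".

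The diary template is in Appendix III. Its introduction reads: "This is a calendar on which you are to record the time and number of pills you take each day for the study". In the grid, the exemestane pill-number cell holds 1 on each of days 1 to 28. The date cells, the exemestane time cells, both entinostat/placebo columns and the notes space are blank.

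**The concern.** The form asks the patient to record a number and has already filled in the answer for perfect adherence. After a missed dose the printed 1 stays unless someone alters it. Appendix III does not ask the patient to alter it; its only instruction on missed pills is that they are not taken later. The printed figure is not needed as a dosing reminder, because the page states one pill per dose above the grid.

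Nor do the documents say how staff should score a row that shows the printed 1 but no date or time. Section 9.7 adds that the timing of doses plays no part in adherence. That statement concerns the score, but it leaves staff without a stated reason to look at the time cells.

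Any resulting error goes in one direction, towards high adherence. At stake are the exemestane results in Section 9.7.2: the category proportions, the plot by cycle, and the Fisher test of whether adding entinostat affects adherence to the backbone drug.

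**Working it through.** **The plan's own figures.** Section 9.7.1 states 84% power for 75% versus 86% high adherence (Fisher's exact test, one-sided 2.5%) and a 95% confidence interval no wider than 0.13 with 240 patients. Exact enumeration with 240 per arm (the plan gives 240 for arm A; the same is assumed for arm B) yields power 0.839. The widest exact interval is 0.130. Both figures reproduce and neither is disputed. They concern entinostat/placebo; no power is stated for exemestane.

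**Position of the printed 1.** The heading row for days 1 to 19 is broken in the extracted text. The heading for days 20 to 28 is intact and puts the 1 under the exemestane pill number. The same layout holds in all 28 rows.

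**Score if nothing is altered.** With m missed doses per 28-day cycle on average, the true score is (28 − m)/28. An untouched form gives 28/28 = 100% whatever m is. The cut-offs are 0.85 × 28 = 23.8 doses and 0.65 × 28 = 18.2 doses.

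| Missed per cycle | True score | True category | Untouched form |
|---|---|---|---|
| 4 | 24/28 = 85.7% | high | 100%, high |
| 5 | 23/28 = 82.1% | medium | 100%, high |
| 9 | 19/28 = 67.9% | medium | 100%, high |
| 10 | 18/28 = 64.3% | low | 100%, high |

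The category changes once misses average 5 or more per cycle.

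**Score if some misses are corrected.** Let f be the share of missed doses left as printed. The recorded score is (28 − m(1 − f))/28, and it exceeds 85% when m(1 − f) < 28 − 23.8 = 4.2.
- m = 5: 1 − f < 0.84, so f > 0.16 moves the patient from medium to high.
- m = 10: 1 − f < 0.42, so f > 0.58 moves the patient from low to high.

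**Effect on the comparison of arms.** Suppose a share u of patients who are truly not high are recorded as high, equally in both arms. The recorded proportion not high in each arm is (1 − u) times the true one, so the difference between arms also shrinks by (1 − u). The plan gives no exemestane rates. Borrowing its 75% versus 86% purely as an illustration, 25% and 14% are not high:
- u = 0: 25 − 14 = 11 points.
- u = 0.5: 12.5 − 7 = 5.5 points.
- u = 1: 0 points.

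The documents do not show where in this range u lies.

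**The case against.** The strongest reply is that the plan never tells staff to add up printed digits. Section 6.2.4 refers to pills noted as taken, and Section 9.7 to doses taken, which leaves room for judgement. A missed dose should leave the time blank, perhaps the date too, and the patient may write a note. The treatment form and the Forms Completion Guidelines are not in the documents and may deal with such rows. Appendix III also lets sites use another calendar format, so some patients may never see this grid.

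The consequence is limited as well. Section 9.7.1 makes entinostat in arm A the primary adherence analysis and powers only entinostat versus placebo. A Medication Adherence Scale form is completed separately for exemestane. Exemestane held for more than 7 days takes the patient off protocol treatment, so an average of 10 misses per cycle implies scattered misses or short gaps, not one long hold.

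All of this stands, and it limits how far the point reaches. It does not remove the fault in the template. Blank cells can flag a missed dose, but no instruction in the documents says that they do. The scale serves to explain non-adherence and does not enter the score.

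A reader might also infer that the agreement check against the Medication Adherence Scale is undermined. Section 9.7.2 words that check for the pill-count method, which is the entinostat/placebo method, so the inference is not supported.

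**Conclusion.** The point holds as a weakness of the template and a missing scoring instruction. At sites using the Appendix III calendar, exemestane doses that were missed may be recorded as taken, and the error can only raise the score. For a patient whose form is left untouched, it is enough to turn a true 82.1% or 64.3% into 100%.

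A reader might go further and conclude that exemestane adherence will sit at its ceiling in both arms. The documents do not support that: some patients will correct the form, some staff may act on blank rows, and some sites may use another calendar. The share affected is unknown.

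The conclusion assumes that the grid is issued as printed and that staff may accept an unaltered entry. The weakening of the comparison further assumes similar form-filling in both arms, which is reasonable under blinding. The effect is confined to the exemestane part of a secondary objective. The entinostat adherence analysis, PFS and OS are unaffected, and no sample size or power figure changes.

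**What to change.** 1. In Appendix III, leave the exemestane pill-number cells blank, as the entinostat/placebo cells already are, or replace them with a taken yes/no box. Tell patients to enter 0 for a missed dose.
2. For calendars already completed on the pre-printed form, report exemestane adherence two ways: entries as they stand counted as taken (upper bound), and only rows with a time counted as taken (lower bound). The second alone would create the opposite bias, because a dose taken without a noted time would count as missed. The true value lies between them if patients neither enter a time for a dose not taken nor strike out one that was.
3. Record which form each patient used.

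A count of returned exemestane tablets is an optional cross-check, not a required change. The Directions page says "Please bring the empty bottle or any leftover tablets and your pill calendar to your next clinic visit", but the calendar page names only the entinostat/placebo bottle and Section 9.7 asks for no exemestane count, so this would be a new procedure.

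The cost is one revised patient form and a second tabulation. The small downside is a change of form part-way through the trial, which step 3 makes traceable.
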